14.0 CLI		
17.1	- I UINU NO OUNCE	

MLHC study Version date: 28/05/2024

14.2	CONFLICT OF INTEREST	27
15.0 PU	BLICATION POLICY/DATA SHARING	27
15.1	FUTURE SECONDARY USE OF DATA	45
16.0 RF	FERENCES	27

MLHC study Version date: 28/05/2024

STATEMENT OF COMPLIANCE

This clinical trial will be carried out in accordance with the following:

- International Conference on Harmonisation Good Clinical Practice (ICH GCP)
- Tri-Council Policy Statement 2018 (TCPS 2)
- Personal Health Information Protection Act (PHIPA), 2004; Chapter 3 Schedule A (PHIPA) and applicable regulations
- Institutional and REB policies and procedures

/_/_:	
/ //	May 6 th , 2024
Signature of PI	Date

LIST OF ABBREVIATIONS

Include a list of abbreviations used within the research protocol. A sample list is included below:

AE Adverse Event

CRE Certified Respiratory Educator

COPD Chronic Obstructive Pulmonary Disease

CRF Case report form(s)

DSMB Data Safety & Monitoring Board

GCP Good Clinical Practice

ICF Informed consent form

MLHC My Lung Health Coach

PHI Personal Health Information

PHIPA Personal Health Information Protection Act

PI Principal Investigator

QI Qualified Investigator

SAE Serious Adverse Event

SUSAR Suspected unexpected serious adverse reaction

TCPS 2 Tri-Council Policy Statement

CLINICAL TRIAL SUMMARY

Short Title	MLHC clinical study
Phase	Pilot study
Methodology	Single arm pilot study
Clinical trial Duration	12 months
Participating site(s)	Single site – Women's College Hospital
Objectives	To evaluate the feasibility and effectiveness of MLHC, a COPD self-management and education support program delivered virtually with an electronic patient-record integrated companion app
Number of Participants	50
Study Intervention Reference Therapy/Comparator	The intervention will be enrollment in the MLHC program (a COPD self-management and education support program delivered virtually), and access to the Epic Care Companion MLHC companion app. There will not be a control group for this pilot study.
Duration of Intervention	12 weeks intervention duration, 6 months total follow-up

Feasibility outcomes (system use): Number of patients who started program over total offered Number of patients who completed program over total started Number of providers who referred patients to the program over total App use metrics over duration of study participation Effectiveness outcomes (clinical outcomes): These outcomes will be collected prior to program commencement, at program completion (3 month), and at 6-month follow-up. Outcomes will be collected by MLHC certified respiratory educators (CREs) using a standardized form in Salesforce, as well as a research assistant based on Epic electronic chart review. For continuous variables, difference in the mean (SD) will be calculated at 3 months and 6 months compared to baseline. For dichotomous variables, difference in proportions at 3 and 6 months compared to baseline will be calculated. Healthcare system utilization: number of COPD-Statistical related outpatient visits, hospital admissions, ED Methodology visits, ICU admissions (at baseline will be over the previous 12 months) o COPD severity: CAT and mMRC scores, and number of COPD exacerbations Health-related quality of life: CAT score Medication, smoking, vaccination status: COPD

controller medication use, oxygen therapy, oral corticosteroid use, antibiotic use, rescue inhaler use, packs per year smoking, smoking cessation

Knowledge of COPD: Adapted COPD-Q scoreSelf-efficacy: Adapted COPD Self-Efficacy Scale

Self-management: Partners in Health Scale (PIHS)

Referrals: pulmonary rehab, smoking cessation

attempts, routine vaccinations

counseling, specialist care

(COPD SES) score

score

MLHC study

1.0 INTRODUCTION

1.1 Background

Chronic Obstructive Pulmonary Disease (COPD) is a highly prevalent chronic airways disease that affects 1 in 9 adults in Ontario. COPD can cause significant symptoms of dyspnea, chronic cough, and wheezing, and lead to important reductions in health-related quality of life. People with COPD can also experience repeated acute exacerbations of their chronic disease, where symptoms worsen for days to weeks, leading to further loss of lung function and quality of life, increased healthcare resource utilization, and mortality. Up to 50% of people with COPD will have an exacerbation within the first year of follow-up, and among those who experience exacerbations, >50% have 2 or more each year. In Canada, COPD exacerbations are one of the leading causes of emergency room visits and hospitalizations nationally (~90,000 hospital admissions yearly, with >25,000 in Ontario alone), and COPD costs the healthcare system \$1.5B annually. As COPD prevalence is increasing yearly, these numbers are unfortunately projected to further grow over time.

Managing COPD and preventing exacerbations can be extremely challenging, as disease progression is often heterogeneous, and symptoms can fluctuate significantly over time. There are also several important patient-level barriers to reducing COPD exacerbations, including lack of medication adherence, limited participation in smoking cessation counseling, low health literacy levels, and poor COPD action plan use. Many of these barriers are related to a lack of effective self-management, a crucial part of holistic COPD care. Self-management refers to the skills and behaviours required for people with COPD to cope with their disease and preserve their quality of life and function. This can include knowledge and skills related to medication adherence and inhaler technique, smoking cessation, physical activity and exercise, managing symptoms and self-recognition of exacerbations, healthy diet, and stress management. 18,20

Interventions to improve COPD self-management are an essential part of COPD care. However, many patients with COPD do not have access to self-management interventions, and poor self-management behaviour (including low adherence to medications and action plans, lack of exercise maintenance, and low health literacy levels) remains an important care gap in COPD. In Ontario, there is currently no uniformly available pathway for patients with COPD to access evidence-based self-management interventions, and individual providers lack the time and resources necessary to provide effective self-management support to all of their patients.

1.2 Study Intervention

My Lung Health Coach (MLHC) is a freely available evidence-based and person-centered COPD self-management program that connects people virtually with experienced certified respiratory educators (CREs) to provide structured COPD education and self-management support. MLHC was jointly developed by the Lung Health Foundation (a charitable organization focused on lung health advocacy) and academic Respirologist [name], with input from community members living

MLHC study

with COPD. MLHC links community members living with COPD with certified respiratory health educators, using a person-centered approach to provide COPD education and self-management support. It is delivered virtually through one-on-one meetings offered over multiple sessions over 12 weeks. The topics covered in the program include: general COPD knowledge, smoking cessation, COPD medications (inhalers, oxygen), physical activity counseling, mental health and wellness, vaccinations, symptom self-management skills (breathing, energy management, symptom monitoring), nutrition, travel, and long-term planning (including end-of-life care).

In order to improve the patient experience using MLHC, we have integrated the MLHC program into the Epic Care Companion app at Women's College Hospital, an interactive patient facing app designed as an extension of the Epic electronic health record system. Using Care Companion, patients will be able to track their progress through MLHC, accomplish session specific educational and self-management tasks, and share their progress with their Women's College healthcare teams.

1.3 Preclinical Data to Date

We are currently testing the MLHC Care Companion app through a rapid cycle design process, to optimize app usability and acceptability. This is being accomplished using an iterative end-user testing process with patient focus groups and qualitative and quantitative assessments. This process is approved as a quality improvement project (APQIP # 2024-0015-P)

1.4 Clinical Data to Date

n/a

1.5 Risk s/Benefits

The intervention being offered is patient education and self-management support program, developed in line with international COPD guidelines. A recent Cochrane review of COPD self-management and support programs (Schrijver et al. 2022) reported that these types of interventions are unlikely to cause harm. However, potential harms that may occur could include poor management of care by CREs (however this is unlikely as the CRE is a licensed and regulated clinical professional), risk of data breach through the use of the Care Companion smartphone app (again this is unlikely given the app is operated through high security protocols within Women's College), and risk of embarrassment if personal health information is inappropriately released.

The virtual format of this program is unlikely to confer any additional risk, as the format of self-management and education support is not specified in international and national guidelines, only the content delivered.

In terms of benefits, the same review found that these types of interventions were associated with improved health-related quality of life and a reduction in respiratory-related hospital admissions in COPD. These types of interventions also reduced anxiety and depression levels.

MLHC study

2.0 CLINICAL TRIAL OBJECTIVES

2.1 Primary Objective

The primary objective is to evaluate the feasibility of delivering the MLHC program accompanied by the Epic Care Companion application. This will be evaluated by assessing system use over the study period, including the number of patients who start the program (over total number referred/offered), the number of patients who complete the program over the total number started, and the number of providers who refer patients to the program over the total number of eligible providers. We will also evaluate app use metrics by patients (number of interactions with the app, number of tasks completed, app features activated, time spent using the app)

2.2 Secondary Objective

The secondary objective is to assess for potential clinical benefits of participating in the MLHC program accompanied by the Epic Care Companion application. To assess this we will evaluate healthcare system utilization, COPD severity, health related quality of life, COPD medication use, smoking status, vaccination status, COPD knowledge, self-efficacy scores, self-management scores, and healthcare provider referrals prior to using the program vs. after program completion.

3.0 CLINICAL TRIAL DESIGN

3.1 Overall Design

This pilot study will be a single center, single arm, pilot trial. There will not be a control group. Each participant will complete the 12-week MLHC virtual program, during which time they will also interact with the Care Companion app. Clinical outcomes will then be reassessed at 6 months after study initiation. The trial is expected to last 12 months.

3.2 Primary Endpoints

Feasibility endpoints:

- MLHC program participation
 - o Number of patients who started program over total offered
 - Number of patients who completed program over total started
 - Number of providers who referred patients to the program over total
- MLCH Care Companion app use
 - Number of times app opened
 - Number of sessions accessed within the app
 - Number of session tasks marked completed
 - Use of other app features (ex: medication reminder notifications)
 - Time spent using the app each time used

3.3 Secondary Endpoints

Clinical endpoints:

MLHC study

- Assessed prior to study start, at 3 months (end of MLHC program) and at 6 months (follow-up after program completion). Outcomes will be collected by MLHC CREs using a standardized form in Salesforce, as well as a research assistant based on Epic electronic chart review. For continuous variables, difference in the mean (SD) will be calculated at 3 months and 6 months compared to baseline. For dichotomous variables, difference in proportions at 3 and 6 months compared to baseline will be calculated.
 - Healthcare system utilization (number of COPD-related outpatient visits, hospital admissions, ED visits, ICU admissions (at baseline will be over the previous 12 months)
 - COPD severity (CAT and mMRC scores, and number of COPD exacerbations)
 - Health related quality of life (CAT score)
 - COPD medication use (COPD controller medication use, oxygen therapy, oral corticosteroid use, antibiotic use, rescue inhaler use)
 - Smoking status (packs per year, quit attempts)
 - Vaccination status (routine guidelines recommended vaccines received)
 - COPD knowledge (Adapted COPD-Q score)
 - Self-efficacy score (Adaptd COPD Self-efficacy scale score)
 - Self-management score (Partners in Health Scale score)
 - Healthcare provider referrals prior to using the program (pulmonary rehab, smoking cessation counseling referrals

4.0 PARTICIPANT SELECTION AND WITHDRAWAL

4.1 Target Population

Patients with physician diagnosed COPD will be the target patient population.

4.2 Participant Recruitment and Screening

We will target a recruitment of 50 patients with physician diagnosed COPD. The patients will be recruited from the WCH Respirology Program clinics (as patients must be followed at WCH in order to use the Epic Care Companion app component). Recruitment will be accomplished through: advertisement posters in the Respirology clinic directing patients to discuss participation with their WCH Respirologist, and referrals from clinicians/circle of care. The potential participant's respirolgist will be the one to determine interest/consent in the participant being contacted for the study.

Participants who have expressed interest in the study will be contacted by study personnel (for example, a research assistant) to discuss potential participation in the study. Patients will not be compensated for their participation.

4.3 Equity, Diversity and Inclusion Considerations

We will consider patient gender during study recruitment, and collect this information on study enrollment. As this is a small pilot study, it will likely not be possible to meaningfully analyze study results in a disaggregated manner based on gender.

MLHC study

4.4 Eligibility Criteria

4.4.1 Inclusion Criteria

The participant must meet all of the inclusion criteria to eligible for this clinical trial:

- 1. Must be deemed to have capacity to provide informed consent;
- 2. Must sign and date the informed consent form;
- 3. Stated willingness to comply with all study procedures;
- 4. Be diagnosed with COPD as per a WCH Respirologist
- 5. Be 40 years or older
- 6. Be a current or ex-smoker
- 7. Have a history of at least 1 COPD exacerbation (requiring prednisone or antibiotic use, or an urgent healthcare visit of any kind) in the previous 12 months

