4.4.2 Exclusion Criteria

An individual who meets any of the following criteria will be excluded from participation in this clinical trial:

- 1. Experienced a COPD exacerbation in the 4 previous weeks to study enrollment
- 2. Co-diagnosis of asthma by a WCH Respirologist
- 3. Significant co-morbidities that could interfere with program participation, or terminal illness
- 4. Willing to download and use the Epic Care Companion app and has a suitable mobile device to do this
- 5. Pregnancy

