5.6 Concomitant Therapy

COPD medication use/treatments (inhalers, antibiotics, prednisone, and oxygen) will be recorded at baseline, at 3 months follow-up, and at 6 months follow-up.

5.7 N/A	Packaging
5.8 N/A	Blinding of Study Intervention
5.9	Receiving, Storage, Dispensing and Return
5.9.1 N/A	Receipt of Study Intervention Supplies
5.9.2 N/A	Storage
5.9.3 N/A	Dispensing of Study Intervention
5.9.4 N/A	Return or Destruction of Study Intervention

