7.4.3 Analysis of the Secondary Endpoint(s)

Clinical endpoints:

Assessed prior to study start, at 3 months (end of MLHC program) and at 6 months (follow-up after program completion). Outcomes will be collected by MLHC CREs using a standardized form in Salesforce, as well as a research assistant based on Epic electronic chart review. For continuous variables, difference in the mean (SD) will be calculated at 3 months and 6 months compared to baseline. For dichotomous variables, difference in proportions at 3 and 6 months compared to baseline will be calculated.

MLHC study

- Healthcare system utilization (number of COPD-related outpatient visits, hospital admissions, ED visits, ICU admissions (at baseline will be over the previous 12 months)
- COPD severity (CAT and mMRC scores, and number of COPD exacerbations)
- Health related quality of life (CAT score)
- COPD medication use (COPD controller medication use, oxygen therapy, oral corticosteroid use, antibiotic use, rescue inhaler use)
- Smoking status (packs per year, quit attempts)
- Vaccination status (routine guidelines recommended vaccines received)
- COPD knowledge (Adapted COPD-Q score)
- Self-efficacy score (Adapted COPD Self-efficacy scale score)
- Self-management score (Partners in Health Scale score)
- Healthcare provider referrals prior to using the program (pulmonary rehab, smoking cessation counseling referrals

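### Entry selects on exacerbations in the same 12 months that form the utilization baseline, so the uncontrolled before-after change in urgent COPD care cannot be read as the effectiveness outcome the summary calls it

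*Protocol*

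**What the plan says.** - **Entry.** Protocol 4.4.1, item 7: "Have a history of at least 1 COPD exacerbation" in the previous 12 months. Prednisone, antibiotics or an urgent healthcare visit each qualify an event. Section 4.4.2, item 1, excludes a patient who "Experienced a COPD exacerbation in the 4 previous weeks to study enrollment".
- **Design.** Section 3.1: "There will not be a control group".
- **Outcome.** Sections 3.3 and 7.4.3 report the change from baseline at 3 and 6 months. For utilization (outpatient visits, admissions, ED visits, ICU admissions) the window "at baseline will be over the previous 12 months". For "COPD severity (CAT and mMRC scores, and number of COPD exacerbations" no window is given for the exacerbation count.
- **Label.** The Clinical Trial Summary gives the objective as "To evaluate the feasibility and effectiveness of MLHC" and files these measures under "Effectiveness outcomes (clinical outcomes". Section 2.2 is softer and speaks of potential benefit.
- **Caveats.** Section 7.1 states no hypothesis. Section 7.2 says the study is not powered for clinical differences and that its results will inform the sample size of a controlled trial. Section 8.5 repeats the point on power.

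**The concern.** Patients are chosen partly on the quantity whose change is then reported. An urgent visit for COPD can itself qualify a patient for entry, and it also counts in the 12-month utilization baseline. Requiring at least one event raises the baseline count above these patients' usual level. The 4-week exclusion works the other way, because it forces an event-free month into the baseline and also selects patients with lower rates. The net shift is an artefact of entry. Annualising does not remove it, and a larger sample would not shrink it.

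Two things are at stake. A lower rate of urgent care after the program could be reported as effectiveness when selection explains some or all of it. Also, section 7.2 does not say which results will feed the next trial's sample size, and section 10.1 says the effectiveness measures are meant to inform larger trials. If the before-after change became the target difference, the bias would enter that calculation.

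**Working it through.** The plan gives no figure for this change, so there is none to reproduce. The check asks what change is expected when the program does nothing.

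**Inputs from the Protocol.** At least 1 event in the past 12 months (4.4.1); none in the last 4 weeks, w = 28/365 = 0.0767 year (4.4.2); 50 patients (7.2). Section 1.1 says that up to 50% of people with COPD have an exacerbation in the first year and that more than 50% of those have 2 or more a year. Both are bounds, and they describe COPD generally, whereas patients here come from hospital respirology clinics (4.2).

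**Assumptions.** Each patient has a constant rate. Rates follow a gamma distribution across patients (negative binomial counts) with shape k, scale θ and mean μ = kθ. There is no program effect, follow-up is complete and rates are annualised.

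**Formula.** Let D(t) = kθ(1 + θt)^(−k−1) and R = D(1)/D(w). For a baseline look-back of T years (w < T ≤ 1):

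follow-up rate / baseline rate = (1 − R) × T / (T − w)

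The sign of the change switches at T = w/R.

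**Worked case, 50%/50%** (share with any event / share of those with 2 or more). Here k = 1 and θ = 1. D(1) = 2^(−2) = 0.250, D(w) = 1.0767^(−2) = 0.863 and R = 0.290. With T = 1 the ratio is 0.710/0.923 = 0.769, a change of −23.1%.

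| Any / 2+ | μ, k | Rate per year, baseline to follow-up (T = 12 months) | T = 12 months | T = 6 months | T = 3 months |
|---|---|---|---|---|---|
| 50%/50% | 1.00, 1.00 | 1.86 to 1.43 | −23.1% | −16.1% | +2.5% |
| 50%/60% | 1.36, 0.57 | 2.36 to 2.06 | −12.5% | −4.5% | +16.6% |
| 70%/70% | 2.33, 1.00 | 2.83 to 2.68 | −5.2% | +3.3% | +26.2% |
| 50%/70% | 2.21, 0.35 | 3.22 to 3.08 | −4.3% | +4.4% | +27.5% |
| 50%/75% | 3.23, 0.27 | 3.86 to 3.81 | −1.3% | +7.7% | +31.5% |
| 50%/80% | 5.66, 0.21 | 4.59 to 4.63 | +0.8% | +10.0% | +34.3% |

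With k = 1, the 12-month change reaches zero at about 78%/78%, a mean of 3.6 events per year. In the first three rows the sign switches at look-backs of about 3.2, 4.8 and 7.4 months.

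**Urgent visits.** If a fixed share q of exacerbations leads to an urgent visit, both rates are multiplied by q and the expected relative change is the same. Visits not caused by exacerbations dilute it.

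**What 50 patients would show.** These are simulated trials with no effect, a 12-month baseline and an annualised 6-month follow-up. A fall in exacerbations appears in about 93%, 80% and 64% of trials for the first three rows. For urgent visits with q = 1/4 (assumed), it appears in about 74%, 64% and 56%. For the last three rows the urgent-visit figures are about 55%, 52% and just under one half.

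**The case against.** The strongest reply is that the direction is not established. That stands. The −23% needs exactly 50% with repeat events, whereas section 1.1 says more than 50%, so that case is the boundary and gives the largest fall in the table. Clinic patients may well have more repeat events than people with COPD generally. A reader might infer that a fall is to be expected, or that nearly every null trial would show one. The documents do not support either: the 12-month window is fixed for utilization only, and with frequent repeat events the expected change is near zero or slightly positive.

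A second reply is that the body of the Protocol is already careful. Sections 3.3 and 7.4.3 call these clinical endpoints, section 2.2 speaks of potential benefit, nothing is tested, and a controlled trial is to follow. This lowers the weight. It does not answer the point, because those caveats concern testing and precision, not a systematic shift caused by entry.

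A third reply is that analysis detail may sit in a statistical analysis plan that is not shown. That is fair for the coding of steroid and antibiotic use and for the safety comparator in section 7.4.4, and neither is pressed here. A reader might also infer that the bias hides a safety signal. Section 7.4.4 names no comparator, and sections 8.2 and 8.5 provide for event recording and case-by-case discussion, so that inference is not supported. The entry rule, the utilization window, the before-after comparison and the label, however, are all fixed in the Protocol itself.

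**Conclusion.** The concern holds as a bias in interpretation. The before-after change in ED visits and admissions is distorted by entry selection and cannot be attributed to the program. The same applies to the exacerbation count, with the direction depending on its unstated look-back. With a 12-month look-back and no effect, the illustrative change runs from about −23% to about zero. A fall is the more usual direction but not assured, and shorter look-backs can turn it into an apparent rise. These sizes rest on the negative binomial model, constant individual rates and assumed event frequencies. The presence of the distortion rests on the Protocol's own entry rules and baseline window. The case is weaker for routine outpatient visits and ICU admissions. Severity is low to moderate: the endpoints are secondary in a feasibility pilot with no test.

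**What to change.** 1. In the Clinical Trial Summary, replace the effectiveness label for these outcomes with the potential-benefit wording of section 2.2.
2. In sections 3.3 and 7.4.3, make on-study rates per person-year with 95% confidence intervals the main summary for exacerbations and COPD-related urgent utilization. Keep the before-after change as descriptive and add: *Because entry depends on exacerbations in the previous 12 months and in the last 4 weeks, a change from baseline in these counts can occur without any program effect and will not be interpreted as an effect of the program.*
3. In section 7.2, state that the future sample size will use the on-study event rate, dispersion and attrition, and will not use the before-after change in event outcomes as the target difference.

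The cost is wording only, with no new visits, instruments or patients. The downside is that the pilot gives up a before-after reduction in urgent care as evidence of effect.
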